2.2. Benefit Assessment

By receiving GSK's quadrivalent seasonal influenza vaccine as part of their standard medical care, the subject may have the benefit of being protected against seasonal influenza.

2.3. Overall Benefit:Risk Assessment

The decision to receive GSK quadrivalent seasonal influenza vaccine is made between the healthcare professional (HCP) and the subject, weighing the potential benefits and risks as part of standard medical care.

3. OBJECTIVES

3.1. Primary Objective

- To estimate, in each country and overall, the cumulative percentages of subjects reporting AEIs and/or other AEs within 7 days following vaccination with GSK's quadrivalent seasonal influenza vaccine using adverse drug reaction (ADR) cards.

Refer to Section 10.1.1 for the definition of the primary endpoints.

3.2. Secondary Objectives

- To estimate, in each country and overall, the weekly percentages of subjects reporting AEs and/or other AEs within 7 days following vaccination with GSK's quadrivalent seasonal influenza vaccine using ADR cards, overall, by age strata (6 months to 17 years; 18 to 65 years; >65 years), and risk status (at risk/not at risk).
- To estimate, in each country and overall, the cumulative percentages of subjects reporting AEs and/or other AEs within 7 days following vaccination with GSK's quadrivalent seasonal influenza vaccine using ADR cards, by age strata (6 months to 17 years; 18 to 65 years; >65 years), and risk status (at risk/not at risk).

Refer to Section 10.1.2 for the definition of the secondary endpoints.

4. STUDY DESIGN OVERVIEW

Protocol waivers or exemptions are not allowed unless necessary for the management of immediate safety concerns. Therefore, adherence to the study design requirements, including those specified in the outline of study procedures (Section 7), are essential and required for study conduct.

- Type of design: multi-country, multicentre, prospective, passive enhanced safety surveillance (ESS) study
- This is a Targeted Safety Study (TSS)
- Study population: subjects aged 6 months or above in Spain and aged 18 years or above in Belgium and Germany, and receiving GSK's quadrivalent seasonal influenza vaccine according to the local prescribing information
- Biological samples: Not applicable
- Sampling schedule: Not applicable
- Type of study: self-contained
- Data collection: Electronic Case Report Form (eCRF)
- Primary completion Date (PCD): PCD is defined as the date of final collection of data for all primary outcomes

Refer to [glossary of terms](#) for the definition of PCD.

- End of Study (EoS): Last Subject Last Visit

Refer to [glossary of terms](#) for the definition of EoS.

- Duration of the study: The study is anticipated to run from 01 October 2018 to 15 January 2019. The recruitment period is anticipated to run for 3 months from 01 October 2018 to 31 December 2018, except for subjects aged <9 years who have not been previously vaccinated against influenza in preceding seasons, for whom the recruitment period will end on 01 December 2018 to allow sufficient time to collect information on the second dose that is expected to occur at least 4 weeks after the first dose. The target sample size is approximately 1,000 vaccinated subjects to be reached before 31 December 2018. The intended duration of the study per subject

will be approximately 8 days for all subjects who have previously been vaccinated against influenza in preceding seasons or aged ≥ 9 years at the time of vaccination, and approximately 36 days for children aged < 9 years who have not previously been vaccinated against influenza in preceding seasons.

- Epoch 001: Prospective data collection starting at Visit 1 (Day 1) and ending at Visit 2 (Day 8 or when the ADR card is returned by mail) for all subjects who have previously been vaccinated against influenza in preceding seasons or aged ≥ 9 years at the time of vaccination, or ending at Visit 4 (Day 36 or when the last ADR card is returned by mail) for children aged < 9 years who have not previously been vaccinated against influenza in preceding seasons). Subjects will have up to 14 days post vaccination to return their ADR card (at the next study visit or by mail).

Table 1 Study groups and epochs foreseen in the study

Study Groups	Number of subjects	Age (Min/Max)	Epochs
Prospective	Approximately 1000	6 months and above	Epoch 001

4.1. Discussion of Study Design

The study is a passive enhanced safety surveillance aiming to collect prospectively AEIs and/or other AEs (see [APPENDIX C](#)) experienced within 7 days post vaccination with GSK's quadrivalent seasonal influenza vaccine, using customized Adverse Drug Reaction cards (see [APPENDIX A](#)). Data will be collected via the HCP or study medical staff who administer the seasonal influenza vaccination or who provide the *informed* consent form and the ADR cards.

After written informed consent/informed assent is obtained from the subject/subject's parent(s)/Legally Acceptable Representative (LAR), an ADR card will be distributed to the enrolled subjects/subjects' parent(s)/LAR who will be asked to complete the card and return this to the HCP (or a member of his/her team) either in person at the next scheduled visit or by mail. Upon return, the card information will be entered into a database using eCRF.

The cards will contain pre-defined AEIs to be reported as well as a free text field to report other relevant AEs experienced by the subjects. Subjects will also have the possibility to indicate that no AE occurred within the 7 days' time window.

5. STUDY POPULATION

5.1. Number of Subjects/Centres

Approximately 1000 vaccinees receiving GSK's quadrivalent seasonal influenza vaccine will be enrolled in this study in Belgium, Germany and Spain.

The number of study subjects (n = 1000) is expected to enable detection of very common ($\geq 1/10$), common ($\geq 1/100$ to $< 1/10$) and uncommon ($\geq 1/1,000$ to $< 1/100$) AEs and/or other AEs.

Refer to Section 10.2 for the additional details of the criteria used in the estimation of sample size.

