10.2. Determination of Sample Size

Approximately 1000 subjects will be enrolled in this study.

Table 4 shows the probability to observe at least one AE, the exact 95% Confidence Intervals (CIs) for the percentage of vaccinated subjects with the AE and Relative Standard Error (RSE) for a range of scenarios in term of number of vaccinated subjects and true percentage of vaccinated subjects with the AE:

- With an overall sample size of 1000 vaccinated subjects (whole study period, all countries) and a true percentage of vaccinated subjects with the AE ranging from 1% to 10%, the corresponding probability to observe at least one vaccinated subject with the AE is >99% and the RSE ranges from 9.5% to 31.5%.
- With an overall sample size of 75 vaccinated subjects (by week, all countries) and a true percentage of vaccinated subjects with the AE ranging from 1% to 10%, the corresponding probability to observe at least one vaccinated subject with the AE ranges from 52.9% to >99% and the RSE ranges from 34.6% to 114.9%.

Table 5 shows the evolution by week of the cumulative probability to observe at least one AE, the exact 95% CI for the cumulative percentage of vaccinated subjects with the AE and RSE in the course of the study for an overall sample size of 1000 (all countries) and 333 (by country) vaccinated subjects and a true percentage of vaccinated subjects with the AE of 1%.

Table 4 Probability to observe at least one AE, exact 95% Confidence Intervals and Relative Standard Error according to number of vaccinated subjects and true percentage of vaccinated subjects with the AE

Number of vaccinated subjects	True percentage of vaccinated subjects with the AE (%)	Probability ^s to observe ≥1 vaccinated subject with the AE (%)	Number of vaccinated subjects with the AE	Exact 95% CI* on the percentage of vaccinated subjects with the AE		Associated relative standard error (%)
				Lower Limit	Upper limit	
1500 (whole study period, all countries)	10	>99	150	8.53	11.63	7.7
	8	>99	120	6.68	9.49	8.8
	6	>99	90	4.85	7.32	10.2
	4	>99	60	3.07	5.12	12.6
	2	>99	30	1.35	2.84	18.1
	1	>99	15	0.56	1.64	25.7
	0.5	>99	7.5	0.21	1.00	36.4
	0.1	77.7	1.5	0.01	0.43	81.6
1000 (whole study period, all countries)	10	>99	100	8.21	12.03	9.5
	8	>99	80	6.39	9.86	10.7
	6	>99	60	4.61	7.66	12.5
	4	>99	40	2.87	5.41	15.5
	2	>99	20	1.23	3.07	22.1
	1	>99	10	0.48	1.83	31.5
	0.5	>99	5	0.16	1.16	44.6
	0.1	63.2	1	0.00	0.56	99.9
75 (per week, all countries)	10	>99	7.5	4.27	19.12	34.6

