	8	>99	6	2.99	16.60	39.2
	6	99.0	4.5	1.83	13.99	45.7
	4	95.3	3	0.83	11.25	56.6
	2	78.0	1.5	0.14	8.28	80.8
	1	52.9	0.75	0.01	6.65	114.9
500 (whole study period, by country)	10	>99	50	7.51	12.97	13.4
	8	>99	40	5.78	10.73	15.2
	6	>99	30	4.08	8.45	17.7
	4	>99	20	2.46	6.11	21.9
	2	>99	10	0.96	3.65	31.3
	1	>99	5	0.33	2.32	44.5
	0.5	91.8	2.5	0.08	1.59	63.1
	0.1	39.4	0.5	0.00	0.93	141.4
333 (whole study period, by country)	10	>99	33.3	7.00	13.74	16.4
	8	>99	26.6	5.32	11.45	18.6
	6	>99	20	3.70	9.12	21.7
	4	>99	13.3	2.17	6.70	26.8
	2	>99	6.7	0.79	4.15	38.4
	1	96.5	3.3	0.23	2.76	54.5
	0.5	81.2	1.7	0.04	1.99	77.3
	0.1	28.3	0.3	0.00	1.30	173.2
25 (per week, by country)	10	92.8	2.5	1.70	28.67	60.0
	8	87.6	2	0.98	26.03	67.8
	6	78.7	1.5	0.44	23.27	79.2
	4	64.0	1	0.10	20.35	98.0

Number of vaccinated subjects	True percentage of vaccinated subjects with the AE (%)	Probability [§] to observe ≥1 vaccinated subject with the AE (%)	Number of vaccinated subjects with the AE	Exact 95% CI* on the percentage of vaccinated subjects with the AE		Associated relative standard error (%)
				Lower Limit	Upper limit	
	2	39.7	0.5	0.00	17.21	140.0
	1	22.2	0.25	0.00	15.52	199.0

[§] Binomial distribution

* [Clopper, 1934]

Table 5 Cumulative probability to observe at least one AE, exact 95% Confidence Intervals and Relative Standard Error by week for a true percentage of subjects with the AE of 1%

Number of vaccinated subjects	ISO weeks	Cumulative number of vaccinated subjects	Cumulative probability [§] to observe ≥1 vaccinated subject with the AE (%)	Cumulative number of vaccinated subjects with the AE	Average percentage of vaccinated subjects with the AE (%)	Exact 95% CI* on the cumulative percentage of vaccinated subjects with the AE		Associated relative standard error (%)
						Lower Limit	Upper limit	
1000 (whole study period, all countries)	40-40	75	52.9	0	1.00	0.00	4.80	114.9
	40-41	150	77.9	1	1.00	0.02	3.66	81.2
	40-42	225	89.6	2	1.00	0.11	3.17	66.3
	40-43	300	95.1	3	1.00	0.21	2.89	57.4
	40-44	375	97.7	3	1.00	0.17	2.32	51.4
	40-45	450	98.9	4	1.00	0.24	2.26	46.9
	40-46	525	>99	5	1.00	0.31	2.21	43.4
	40-47	600	>99	6	1.00	0.37	2.16	40.6
	40-48	675	>99	6	1.00	0.33	1.92	38.3
	40-49	750	>99	7	1.00	0.38	1.91	36.3
	40-50	825	>99	8	1.00	0.42	1.90	34.6
	40-51	900	>99	9	1.00	0.46	1.89	33.2
	40-52	1000	>99	10	1.00	0.48	1.83	31.5
333 (whole study period, by country)	40-40	25	22.2	0	1.00	0.00	13.72	199.0
	40-41	50	39.5	0	1.00	0.00	7.11	140.7
	40-42	75	52.9	0	1.00	0.00	4.80	114.9

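### Section 5.1 claims detection of uncommon AEs without qualification, but at that class's lower bound of 1/1,000 Table 4 gives only a 63.2% chance of seeing one case

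*Protocol*

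**What the plan says.** Section 5.1 (Number of Subjects/Centres) gives the purpose of the sample size: "The number of study subjects (n = 1000) is expected to enable detection of very common", common and "uncommon ($\geq 1/1,000$ to $< 1/100$) AEs and/or other AEs". All three frequency classes fall under one statement, and the third has its bounds written out, so its lower limit is 0.1%. No probability is attached and no part of the class is set apart. The next sentence points onward: "Refer to Section 10.2 for the additional details of the criteria used in the estimation of sample size".

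Section 10.2 (Determination of Sample Size) reports, for various sample sizes and true frequencies, the binomial probability of at least one affected subject, an exact confidence interval and the relative standard error (RSE); the first of its tables "shows the probability to observe at least one AE". For n = 1000 and true frequencies from 1% to 10%, its text says that "the corresponding probability to observe at least one vaccinated subject with the AE is >99% and the RSE ranges from 9.5% to 31.5"%. Table 4 goes lower. For n = 1000 it has two rows inside the uncommon class:

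- at 0.5%: probability above 99%, 5 expected cases, interval 0.16 to 1.16, RSE 44.6%;
- at 0.1%: probability 63.2%, 1 expected case, interval 0.00 to 0.56, RSE 99.9%.

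There is no row between these two. Neither section states a minimum probability that would count as detection.

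**The concern.** One unqualified word, detection, covers frequencies at which the study is almost certain to see a case and a frequency at which it would see none more than a third of the time. Section 5.1 makes the claim and Section 10.2 is named as its support, so the two should agree over the range that Section 5.1 spells out. At the lower bound they do not sit well together.

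What is at stake is interpretation. Someone relying on Section 5.1 could take the absence of a given event among 1000 vaccinees as informative about frequencies near 1/1,000, when such an absence would be quite likely even if the event occurred at that rate. In a safety surveillance study it is worth avoiding that misreading.

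**Working it through.** **Inputs.** n = 1000 and the class 0.1% ≤ p < 1% are from Section 5.1. The measure, P(at least one case), and its binomial basis are from Section 10.2 and the footnote to Table 4. The protocol gives no detection level, so 80%, 90%, 95% and 99% are used below as assumptions.

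**Step 1: reproduce Table 4 at 0.1%.**

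- P(at least one) = 1 − (1 − p)^n = 1 − 0.999^1000 = 0.632, or 63.2%. This matches.
- Expected cases = 1000 × 0.001 = 1. This matches.
- RSE = √((1 − p)/(n p)) = √(0.999/1) = 99.9%. This matches.
- Exact (Clopper-Pearson) interval for 1/1000 = 0.00% to 0.56%. This matches.
- P(no case) = 1 − 0.632 = 0.368, or about 37%.

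**Step 2: reproduce Table 4 at 0.5%.** 1 − 0.995^1000 = 0.993, consistent with the entry of more than 99%.

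**Step 3: the larger scenario.** With n = 1500 and p = 0.1%, 1 − 0.999^1500 = 0.777. Table 4 shows 77.7%.

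**Step 4: fill the gap between the two rows (n = 1000).**

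| True frequency | P(at least one case) |
|---|---|
| 0.1% | 63.2% |
| 0.2% | 86.5% |
| 0.3% | 95.0% |
| 0.4% | 98.2% |
| 0.5% | 99.3% |

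**Step 5: where the shortfall ends, for an assumed level t.** Solving 1 − (1 − p)^1000 = t gives p = 1 − (1 − t)^(1/1000). The share of the class below that point, on the plain percentage scale, is (p − 0.1)/(1 − 0.1), with p in percent.

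| Assumed level t | Shortfall ends at p | Share of the class below it |
|---|---|---|
| 80% | 0.16% | 0.06/0.9 ≈ 7% |
| 90% | 0.23% | 0.13/0.9 ≈ 14% |
| 95% | 0.30% | 0.20/0.9 ≈ 22% |
| 99% | 0.46% | 0.36/0.9 = 40% |

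At 0.1% the probability is below all four levels. On this scale most of the class is supported under any of them.

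**Step 6: unreturned cards.** The figures above assume that all 1000 subjects supply data. The primary analysis uses the Safety Set (Sections 10.3.3 and 10.6), which includes subjects who received a card but did not return it, and Section 10.4 counts subjects who report nothing as having had no event. As an illustration, if 80% of cards came back (an assumed rate), 1 − 0.999^800 = 55.1% at 0.1%. The 63.2% is therefore a best case.

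**The case against.** The strongest reply is that there is no stated criterion to contradict. The protocol never defines detection by a minimum probability. At 1/1,000 the table expects one case, and seeing at least one is more likely than not; elsewhere in the class the expected count is higher. The bracketed limits can be read as merely defining the term uncommon, without promising anything at every frequency inside it. Section 5.1 also refers straight on to Section 10.2, where the 63.2% is printed for exactly this n and this frequency, so nothing is hidden.

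Much of this stands. With no threshold set, only the 0.1% figure comes from the protocol itself. A reader might infer that Section 10.2 shows the claim to be overstated from 0.1% to about 0.3%; it does not, because that upper end appears only once a 95% level is assumed. Nor may one infer that the claim fails for uncommon events in general: Table 4 shows more than 99% at 0.5%. That the text of Section 10.2 speaks only of 1% to 10% is also not evidence against lower frequencies, since it summarises a table that goes lower.

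Two parts do not stand. Showing the 63.2% in Table 4 does not narrow the broader sentence in Section 5.1; it is what reveals the mismatch. And reading detection as anything better than even odds would place probabilities of more than 99% and of 63% under the same unqualified word, which tells the reader little about what the study can show.

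**Conclusion.** The point holds at the low end of the uncommon class. At the bound that Section 5.1 names, n = 1000 gives a 63.2% chance of observing any case, by the protocol's own table. This rests on the binomial model of Section 10.2 and on full card return. The extent above 0.1% depends on the assumed level in Step 5 and should always be quoted with that level.

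It is a mismatch between a stated capability and its cited support, not a calculation error: every Table 4 entry checked here reproduces. A reader might also infer that the sample size is inadequate. The documents do not support that. Section 10.9 makes all analyses descriptive, Section 10.10.2 says there is no hypothesis testing, and no decision rule depends on observing a case at 1/1,000. Severity is low and the change is optional, though worth making. Confidence in the corrected statement is high.

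**What to change.** In Section 5.1, replace the unqualified claim for the uncommon class with the probabilities themselves, for example:

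> Assuming all ADR cards are returned, n = 1000 gives >99% probability of observing at least one case of an AE with a true frequency of 5/1,000 or more, and 63% at 1/1,000 (Table 4).

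Both figures are already in Table 4, so no detection level has to be chosen. The cost is one sentence. Sample size, endpoints and analyses stay as they are, and the only downside is a less favourable stated capability.

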5.2. Inclusion Criteria for Enrolment

Deviations from inclusion criteria are not allowed because they can potentially jeopardise the scientific integrity and regulatory acceptability of the study or subject safety. Therefore, adherence to the criteria as specified in the protocol is essential.

The objective of the study is to cover all age ranges as per GSK's quadrivalent vaccine indication. However, due to feasibility constraints, Belgium and Germany will only recruit subjects 18 years of age and above (German participating sites will target essentially older adults [subjects aged from 50 years onwards]). Spain will target subjects between 6 months and 65 years of age at the time of the vaccination.

All subjects must satisfy ALL the following criteria at study entry:

- Subjects who, in the opinion of the investigator, can and will comply with the requirements of the protocol (e.g., complete the ADR card, return for the next scheduled visit or return the ADR card by mail within a timely manner).
- A male or female subject vaccinated with GSK's quadrivalent seasonal influenza vaccine (one or two dose schedule) according to the routine medical practices between 01 October 2018 and 31 December 2018.
- Subjects aged 6 months or above at the time of the vaccination ***according to the countries' specificities.***
- Written informed consent/informed assent obtained from the subjects/subjects' parent(s)/Legally Acceptable Representative(s) (LARs).

5.3. Exclusion Criteria for Enrolment

Deviations from exclusion criteria are not allowed because they can potentially jeopardise the scientific integrity and regulatory acceptability of the study. Therefore, adherence to the criteria as specified in the protocol is essential.

The following criterion should be checked at the time of study entry. If ANY exclusion criterion applies, the subject must not be included in the study:

- Child in care

Please refer to the [glossary of terms](#) for the definition of child in care.

6. CONDUCT OF THE STUDY

6.1. Regulatory and Ethical Considerations, including the Informed Consent Process

The study will be conducted in accordance with the International Conference on Harmonisation (ICH) Guideline for Good Clinical Practice (GCP), Good Epidemiology Practice (GEP), Good Pharmacovigilance Practice (GVP), or other applicable guidelines, all applicable subject privacy requirements and the guiding principles of the Declaration of Helsinki.

The study has been designed and will be conducted in accordance with the ICH Harmonised Tripartite Guideline for clinical investigation of medicinal products in the paediatric population (ICH E11) and all other applicable ethical guidelines.

GSK will obtain favourable opinion/approval to conduct the study prior to a site initiating the study in that country or will document that neither a favourable opinion nor an approval to conduct the study is needed.

Conduct of the study includes, but is not limited to, the following:

- Institutional Review Board (IRB)/Independent Ethics Committee (IEC) review and favourable opinion/approval of study protocol and any subsequent amendments.
- Subject/ subject's parent(s)/LAR(s) informed consent and subject informed assent, as appropriate.
- Investigator reporting requirements as stated in the protocol.

GSK Biologicals will provide full details of the above procedures to the investigator, either verbally, in writing, or both.

Freely given and written or witnessed/thumb printed informed consent must be obtained from each subject and/or each subject's parent(s)/LAR(s) or the impartial witness and subject informed assent, as appropriate, prior to participation in the study.

GSK Biologicals will prepare a model Informed Consent Form (ICF) which will embody the applicable ICH GCP or other applicable guidelines and GSK Biologicals required elements. While it is strongly recommended that this model ICF be followed as closely as possible, the informed consent requirements given in this document are not intended to pre-empt any local regulations which require additional information to be disclosed for informed consent to be legally effective. Clinical judgement, local regulations and requirements should guide the final structure and content of the local version of the ICF.

In accordance with the ICH Harmonised Tripartite Guidelines for Good Clinical Practice, a subject who can only be enrolled in the study with the consent of his/her parent(s) or LAR (e.g., minors), should be informed about the study to the extent compatible with the subject's understanding and, if capable, the subject should sign and personally date a written informed assent form (IAF). It is required that the assent be signed by each subject, if capable, in addition to the informed consent that is to be signed by his/her parent or LAR. It should be assessed whether an assent is required depending on the age of the study population and the local requirements.

GSK Biologicals strongly recommends that if the subject reaches the age of consent during the study they will be asked to provide consent at the next study visit (if applicable). This procedure should be applied according to local laws and regulations.

The investigator has the final responsibility for the final presentation of the ICF and IAF, respecting the mandatory requirements of local regulations. The ICF and IAF generated by the investigator with the assistance of the sponsor's representative must be acceptable to GSK Biologicals and be approved (along with the protocol, and any other necessary documentation) by the IRB/IEC.

